### 3.6.2 Supplemental Iron Use

In a Phase 2 study of roxadustat, in which study subjects were randomized to either receive no iron, oral iron or IV iron, there was no significant difference in Hb levels in subjects receiving oral iron compared to subjects receiving IV iron. Therefore, based on the mechanism of action of roxadustat and the Phase 2 study results, in subjects randomized to roxadustat, oral iron may be sufficient for iron supplementation.

In this study, oral iron should be allowed as first-line iron supplementation without restrictions, for both study arms. In addition to the scheduled assessments ([Appendix 3](#)), iron indices may be assessed at any time (via central lab) to evaluate iron storage status of the subjects, if considered necessary by the Investigator.

#### 3.6.2.1 Oral Iron Supplementation

All subjects should be encouraged to take oral iron as the first-line iron supplementation during the Treatment Period, except subjects not tolerating oral iron. The dose and frequency are at the discretion of the Investigator. Oral iron supplementation should be started before the subject becomes iron depleted.

#### 3.6.2.2 Intravenous Iron Supplementation

Intravenous iron supplementation is permitted if in the opinion of the Investigator the subject's Hb has not responded adequately and the subject is considered iron deficient.

Treatment with study medication will continue during IV iron administration. Discontinuation of IV iron is recommended once the subject is no longer deemed iron deficient (eg, ferritin  $\geq 100$  ng/ml [ $\geq 220$  pmol/L], TSAT  $\geq 20\%$ ) and has evidence of a hematopoietic response.

Note: IV iron administration in study subjects during hospitalization is not considered a protocol deviation.

### 3.6.3 Rescue Therapy Guidelines

Rescue therapy guidelines are provided to standardize the use of rescue therapy.

#### 3.6.3.1 Red Blood Cell Transfusion

Red blood cell transfusion should be considered if rapid correction of anemia is required to stabilize the subject's condition (eg, acute hemorrhage) and the Investigator is of the opinion that the blood transfusion is a medical necessity. Study drug treatment may continue during the RBC transfusion administration.

#### 3.6.3.2 Erythropoiesis Stimulating Agents (Roxadustat Arm Only):

The use of ESAs is not permitted during the Treatment Period, except if all of the following criteria are met:

- A subject's Hb level has not responded adequately despite two or more consecutive roxadustat dose increases or the roxadustat dose has reached the maximum dose limit
- Other causes for lack of response or declining Hb, such as iron deficiency, bleeding, acute inflammatory conditions, have been ruled out
- Reducing risk of alloimmunization in transplant eligible patients is a goal.

Roxadustat and ESA may not be co-administered. Treatment with an approved ESA may be initiated  $\geq$  3 days after the last roxadustat dose.

If the situation permits, the Investigator should inform the Medical Monitor prior to initiation of ESA therapy.

Subjects may receive **one course** of ESA rescue during the Treatment Period.

Erythropoiesis-stimulating agent rescue should stop after 4 weeks or once Hb exceeds 9 g/dL, whichever occurs first. If a subject requires more than 4 weeks of ESA rescue therapy due to inadequate Hb response, the Medical Monitor should be contacted.

Treatment with roxadustat may resume after the following intervals:

- Two days after stopping epoetin alfa
- One week after stopping darbepoetin alfa
- Two weeks after stopping methoxy polyethylene glycol-epoetin beta (Mircera®)

If more than one course of ESA rescue is required during the Treatment Period, the subject must be discontinued permanently from the study, and is considered a Treatment Failure.

Inadvertent ESA administration including ESA administration by hospital staff in Roxadustat subjects should not be counted as rescue unless above criteria are met; these subjects may be allowed to continue on study, if considered safe by the Investigator and Medical Monitor.

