
Rescue Therapy and Emergency Procedures:
 
Text was modified as follows:
 
From:
 
Subjects who receive an ESA inadvertently (and do not meet the criteria above) may be allowed to continue on study, if considered safe by the Investigator and Medical Monitor.
 
To:
 
Inadvertent ESA administration, including ESA administration by hospital staff in roxadustat subjects, should not be counted as rescue, unless above criteria are met; these subjects may be allowed to continue on study, if considered safe by the Investigator and Medical Monitor.
 
The following paragraph was updated to (added text is italicized):
 
Subjects may receive one course of ESA rescue during the Treatment Period. Erythropoiesis-stimulating agent rescue should stop after 4 weeks or once Hb exceeds 9 g/dL, whichever occurs first. If a subject requires more than 4 weeks of ESA rescue therapy due to inadequate Hb response, the Medical Monitor should be contacted.
	
ESA therapy is the only standard of care to treat anemia in ESRD patients. It is a common practice to administer ESA during dialysis session. Clarification has been added that inadvertent ESA administration, or ESA administration by hospital staff as part of the standard of care in roxadustat subjects, should not be counted as ESA rescue, unless protocol specified rescue criteria are met.
	
Synopsis; Section 3.6.3.2

Contraception
 
The following section was added:
 
In female subjects of childbearing potential, a serum pregnancy test will be done per the Schedule of Assessments (Appendix 3) to rule out pregnancy. A pregnancy test is not required for female subjects of no childbearing potential eg, postmenopausal (determination whether a woman is post-menopausal is at the discretion of the Investigator), surgically sterile, etc.
	
This language was added to align the protocol with a new SOP for protocol templates
	
Section 3.6.6

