## 7 ENDPOINTS AND ASSESSMENTS

In the endpoint definitions below, rescue therapy for roxadustat treated subjects is defined as ESA rescue or RBC transfusion and rescue therapy for epoetin alfa-treated subjects is defined as RBC transfusion.

All endpoints related to Hb are based on central lab values

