### **8.4.5 Statistical Analysis Plan**

The Statistical Analysis Plan will provide details of the data analyses. As an open-label study the SAP will be finalized prior to accumulation of a substantial amount of data to ensure lack of bias. Any significant changes to the analyses described in this protocol will be highlighted in the SAP and the Clinical Study Report.

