1 INTRODUCTION

This statistical analysis plan (SAP) provides a more technical and detailed elaboration of the statistical analyses of efficacy and safety as outlined and/or specified in the final study protocol. Specifications of tables, figures, and data listings are contained in a separate document (Table shells).

A separate pooled-analysis SAP for pre-specified analysis based on adjudicated composite safety data will complement this study specific SAP. This SAP is based on the Amendment 4 of the protocol dated September 20, 2017.

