4 STUDY ENDPOINTS

4.1 PRIMARY EFFICACY ENDPOINT

There are 2 separate primary endpoints which are defined for US (FDA) submission and Ex-US submission respectively.

US (FDA) submission.

The primary efficacy endpoint for the US submission is the Mean Hb change from baseline (using central laboratory values) to the average level during the Evaluation Period, defined as Week 28 until Week 52. This analysis will be based on the intent-to-treat (ITT) population. Hemoglobin values under the influence of rescue therapy (see definition below) will not be censored for the primary analysis.

Ex-US submission

The primary efficacy endpoint for the Ex-US submission is defined as the proportion of subjects who achieve a Hb response at two consecutive visits at least 5 days apart during the first 24 weeks of treatment, without rescue therapy (see definition below) within 6 weeks prior to the Hb response in the Per Protocol Set (PPS). A Hb response is defined, using central laboratory values, as:

- Hb ≥ 11.0 g/dL and a Hb increase from baseline by ≥ 1.0 g/dL in subjects whose baseline Hb > 8.0 g/dL, or
- Increase in Hb ≥ 2.0 g/dL in subjects whose baseline Hb ≤ 8.0 g/dL.

Rescue therapy for roxadustat treated subjects is defined as recombinant erythropoietin or analogue (ESA) or RBC transfusion, and rescue therapy for Epoetin alfa treated subjects is defined as RBC transfusion. All endpoints using Hb are based on the central lab data.

Baseline Hb is defined as the mean of at least the last 3 available central laboratory Hb values prior to first dose of study medication: three last screening Hb values plus the pre-dose Hb value collected on day 1. In subjects with missing Day 1 Hb value, the mean of three last screening laboratory Hb values will be considered as baseline Hb value.

Hb values from the central laboratory will be sorted by visit date. If two consecutive on-treatment Hb values from the central laboratory meet the Hb response criteria defined by primary efficacy endpoint for the Ex-US submission, the subject will qualify for Hb response as long as there is no rescue therapy 6 weeks before the date of the first of these 2 Hb measurements.

The classification of Hb response shall take into account all consecutive Hb values regardless of whether they are obtained at scheduled or unscheduled visits.

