RBC transfusion is collected in the Blood Transfusions form of the eCRF. The use of ESA is recorded in the related forms of the eCRF and coded into ATC (Code: B03XA01) and generic name.

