The analysis will be repeated with Hb values under the influence of rescue therapy censored. Namely, set Hb to missing for Rescue Medication and 6 weeks afterwards (or 8 weeks if during the evaluation period).

Ex-US Submission: The primary efficacy endpoint for Ex-US submission is defined as the proportion of subjects who achieve an Hb response at two consecutive visits during the first 24 weeks of treatment, without rescue therapy within 6 weeks prior to the Hb response.

- A Hb response is defined, using central laboratory values, as: $Hb \geq 11.0$ g/dL and a Hb increase from baseline by ≥ 1.0 g/dL in subjects whose baseline $Hb > 8.0$ g/dL, or
- Increase in $Hb \geq 2.0$ g/dL in subjects whose baseline $Hb \leq 8.0$ g/dL

Rescue therapy for roxadustat treated subjects is defined as ESA rescue or RBC transfusion, and rescue therapy for epoetin alfa treated subjects is defined as RBC transfusion.

The hypothesis to be tested for the primary efficacy analysis is:

H_0 : Hb response rate for subjects in the roxadustat arm - Hb response rate for subjects in the epoetin alfa arm $\leq -15\%$

Versus

H_1 : Hb response rate for subjects in the roxadustat arm - Hb response rate for subjects in the epoetin alfa arm $> -15\%$

A two-sided 95% CI for the difference of 2 responder rates (roxadustat minus epoetin alfa) based on the Miettinen & Nurminen approach adjusting for treatment and stratification factors will be calculated and this null hypothesis will be rejected if the lower bound of the 95% CI is greater than -15%. Subjects who dropped out from the study without data for the assessment will be treated as non-responder.

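### The SAP states the roxadustat-arm rescue rule in two ways: any ESA in section 4.1, 'ESA rescue' in section 11.1; the 4.1 rule is probably intended and should be made the only one for analysis

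*Protocol*

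**What the plan says.** **SAP 4.1**, which defines the endpoints, says that rescue for roxadustat subjects is "defined as recombinant erythropoietin or analogue (ESA) or RBC transfusion". No reason or criterion is attached. A response counts if there was no rescue in the 6 weeks before the first of two consecutive qualifying Hb values. ESA use is taken from the eCRF and "coded into ATC (Code: B03XA01) and generic name".

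**SAP 11.1.1 and 11.1.2**, which specify the analysis, use different words: "Rescue therapy for roxadustat treated subjects is defined as ESA rescue or RBC transfusion". Protocol section 7 matches them: "rescue therapy for roxadustat treated subjects is defined as ESA rescue or RBC transfusion". So does protocol 8.4.3.1.

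**Protocol 3.6.3.2** permits ESA in the roxadustat arm only if three criteria are all met: inadequate response despite dose increases or at the maximum dose, other causes ruled out, and a goal of reducing alloimmunization risk. It then says: "Inadvertent ESA administration including ESA administration by hospital staff in Roxadustat subjects should not be counted as rescue unless above criteria are met". The rationale given for this clause in the Amendment 4 summary is that such use "should not be counted as ESA rescue, unless protocol specified rescue criteria are met".

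**On precedence**, the SAP introduction says "This SAP is based on the Amendment 4 of the protocol dated September 20, 2017", and protocol 8.4.5 says "Any significant changes to the analyses described in this protocol will be highlighted in the SAP and the Clinical Study Report". The SAP flags no change to the rescue definition.

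**On drug codes**, the SAP 4.4 item on subjects requiring ESA rescue gives only ATC B03XA01. SAP 11.3.4.2 lists B03XA01 (epoetins), B03XA02 (darbepoetin), B03XA03 (Mircera) and B03XA04 (peginesatide). Protocol 3.6.3.2 gives restart intervals after epoetin alfa, darbepoetin and Mircera, so it expects those drugs to be used.

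**The concern.** The two wordings can classify the same subject differently. Suppose that a roxadustat subject receives an ESA from hospital staff, without meeting the three criteria, and within 6 weeks has two consecutive qualifying Hb values. Under SAP 4.1 that pair does not count as a response. Under 'ESA rescue' read with protocol 3.6.3.2 it does.

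Such exposure is foreseen. The Amendment 4 rationale says that ESA is commonly given during dialysis and may be given in hospital, and protocol 3.5.3.3 does not treat hospital ESA as a deviation when roxadustat is not allowed or available there.

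The effect would be one-sided, because only the roxadustat arm has an ESA component of rescue; in the epoetin arm rescue means transfusion under both wordings. The narrow rule can only add roxadustat responders or bring their responses forward. That touches the ex-US primary, the US first secondary and time to first response, in an open-label trial whose responder test is for non-inferiority.

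**Working it through.** **1. The plan's own figure.** Inputs from SAP 5.1 and 11.1.2: 600 subjects randomized 1:1, 80% responders in each arm, margin -15 points, two-sided 95% CI.

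- SE = √(0.8×0.2/300 + 0.8×0.2/300) = 0.03266
- Power = Φ(0.15/0.03266 − 1.96) = Φ(2.633) = 99.6%

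This agrees with the stated power of at least 99%.

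**2. Shift per subject.** Each roxadustat subject reclassified from responder to non-responder moves the difference by 1/300 = 0.33 points. At 500 per arm (about 1000 subjects, SAP 5.1) it is 1/500 = 0.20 points.

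**3. Reclassifications needed to lose non-inferiority.** Unstratified Miettinen-Nurminen two-sided 95% CI, with epoetin observed at 80%:

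| Per arm | Roxadustat v epoetin responders | Difference (points) | Lower bound (points) | Result |
|---|---|---|---|---|
| 300 | 240 v 240 | 0.00 | -6.43 | passes |
| 300 | 216 v 240 | -8.00 | -14.81 | passes |
| 300 | 215 v 240 | -8.33 | -15.15 | fails |
| 500 | 400 v 400 | 0.00 | -4.97 | passes |
| 500 | 352 v 400 | -9.60 | -14.91 | passes |
| 500 | 351 v 400 | -9.80 | -15.12 | fails |

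Starting from equal rates, the verdict changes after 240 − 215 = 25 subjects at 300 per arm, or 400 − 351 = 49 at 500 per arm. The planned interval is stratified and the Per Protocol Set (PPS) will be smaller than the randomized number, so these counts are approximate.

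**4. Effect on power, by assumption.** The documents give no rate of ESA use outside the criteria. Let q be the share of roxadustat subjects who lose responder status under the SAP 4.1 rule, so that their rate is 80% − q. At 300 per arm, power is 98.9% for q = 1%, 97.4% for 2% and 83.6% for 5%. These values of q are illustrations, not estimates.

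**5. How long SAP 4.1 blocks a response.** The block covers pairs whose first value falls within 6 weeks after rescue. On the two-weekly schedule, one ESA dose at Week 8 blocks pairs starting up to Week 14. Visits at Weeks 16, 18, 20, 22 and 24 still leave four consecutive pairs. A response before the dose is untouched. Only subjects with no other qualifying pair by Week 24 are reclassified, so q is smaller than the exposure rate.

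**6. Which analyses are touched.**
- US primary: unaffected, because Hb under rescue is not censored.
- Ex-US primary, US first secondary, time to first response: the narrow rule can only favour roxadustat.
- Ex-US Week 28–36 Hb change and the rescue-censored sensitivity analysis of the US primary: the rule matters, but the direction cannot be determined from the documents.

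**7. Existing protection.** SAP Table 2 item 2 (wrong study drug) does not reach courses of 4 weeks or less before Week 24. Item 4 (prohibited medication) is left to the Medical Monitor. Both act only through the PPS, which the US first secondary does not use. The only alternative responder definition, SAP 4.2.1, ignores rescue altogether and so is more permissive than either wording.

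**The case against.** The strongest reply is that the plan already has one working definition.

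- SAP 4.1 points from the endpoint text to its own definition, then gives the derivation and the eCRF sources. SAP 11.3.4.2, on ESA as rescue, selects log entries by drug code alone.
- No SAP section cites protocol 3.6.3.2 or derives a flag for its criteria, so the narrow reading has no specified implementation.
- The 3.6.3.2 clause sits among conduct rules. It follows the one-course limit and the discontinuation rule, and its sentence goes on to say that such subjects may stay on study. The amendment log lists only the synopsis and 3.6.3.2 as affected, not the endpoint or analysis sections.
- The SAP's silence under protocol 8.4.5 may mean only that its authors took ESA use and ESA rescue to be the same thing.

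Most of this stands. It makes SAP 4.1 the probable intention, and that rule works against roxadustat. It does not remove the conflict: the clause's rationale uses the endpoint's own term, SAP 11.1 repeats that term, and nothing gives SAP 4.1 precedence.

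A further objection also stands. A sensitivity analysis limited to ESA meeting the criteria would require retrospective judgement on adequacy of response, other causes and alloimmunization goals, in an open-label trial. The documents do not say that the eCRF records the reason for ESA.

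A reader might infer that the plan credits ESA-driven responses to roxadustat, or that the non-inferiority conclusion is in doubt. The documents do not support either. The first follows only if SAP 4.1 is set aside. The second needs an observed difference already near the limit, and no exposure rate is given.

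**Conclusion.** There is a real but minor inconsistency in a rule behind the ex-US primary and US first secondary endpoints. SAP 4.1 is probably the intended rule. The narrow wording, if used, would favour roxadustat on the response endpoints, by an amount that cannot be estimated from the documents.

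The non-inferiority verdict would probably not change. From equal 80% rates it would take 25 reclassified roxadustat responders at 300 per arm, or 49 at 500. The choice of wording decides the result only if the observed difference under one of the rules is already near -8 points at 300 per arm (near -9.7 at 500). These figures rest on the plan's 80% rate and on an unstratified interval.

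The ATC codes are a separate, smaller slip. In SAP 4.1 the words 'or analogue' and the coding by generic name may recover the other drugs. The SAP 4.4 item as written would miss darbepoetin and Mircera.

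**What to change.** In the SAP, before database lock:

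1. In 11.1.1, 11.1.2 and the Table 4 footnote, refer to the 4.1 definition, stated for analysis as any ESA (ATC B03XA01 to B03XA04) given to a roxadustat subject, regardless of reason.
2. State that the protocol 3.6.3.2 clause governs conduct (the one-course limit and continuation on study) and not the endpoint.
3. Correct the ATC codes in 4.1 and 4.4 to B03XA01 to B03XA04. Leave the 4.4 item as ESA rescue; counting every ESA there would change what it measures.
4. Report how many roxadustat subjects differ in responder status between the 4.1 and 4.2.1 definitions. Because 4.2.1 also ignores transfusions, this count is an upper limit on the ESA effect, apart from 4.2.1's discontinuation rule. If the two definitions agree, the wording cannot matter.

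A sensitivity analysis based on the 3.6.3.2 criteria is optional, and worth doing only if the eCRF records the reason for ESA.

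The cost is SAP wording and one count from data already collected. The clinical rescue rules stay as they are. The downside is that the roxadustat response rate may be slightly lower than under the narrow wording.

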### 3.6.4 Therapeutic Phlebotomy

If there are clinical concerns of excessive elevation of Hb levels, the Investigator may decide to perform a therapeutic phlebotomy in addition to a dose hold. This should be discussed with the Medical Monitor and documented.

### 3.6.5 Excluded Medications/Therapies/Substances

Subjects are not permitted to consume more than three alcohol-containing drinks per day during the Treatment or Follow-up Periods.

The following medications are prohibited from the day of randomization until completion of the study:

- Androgens and iron-chelating agents (eg, deferoxamine, deferiprone, or deferasirox therapy)
- Dapsone in any dose amount
- For subjects receiving roxadustat: chronic use of acetaminophen or paracetamol >2.0 g/day during the Treatment Period and up to 1 week after EOT.
- Use of herbal medicine is not prohibited but strongly discouraged.

### 3.6.6 Contraception

Female subjects of childbearing potential must agree to practice a dual method of contraception, for example, a combination of the following: (1) oral contraceptive, depo progesterone, or intrauterine device; and (2) a barrier method (condom or diaphragm). Male subjects with female partners of childbearing potential who are not using birth control as described above must use a barrier method of contraception (eg, condom) if not surgically sterile (ie, vasectomy).

Contraceptive methods must be practiced upon entering the study and through 12 weeks after the last dose of study treatment. If a subject discontinues prematurely, the contraceptive method must be practiced for 12 weeks following final administration of study drug.

Pregnancy, spontaneous or therapeutic abortion, or events related to pregnancy must be reported ([Section 9.3.6](#)).

In female subjects of childbearing potential, serum pregnancy test will be done per Schedule of Assessments ([Appendix 3](#)) to rule out pregnancy. Pregnancy test is not required for female subjects of no childbearing potential eg, postmenopausal (determination whether a woman is post-menopausal is at the discretion of the Investigator), surgically sterile etc..

## 3.7 Safety Monitoring Plan

Safety will be assessed throughout the study. A complete baseline profile of each subject will be established through demographics, medical history, clinical laboratory values, vital signs, physical examinations (PEs), and electrocardiogram (ECGs). During the course of the study, vital signs, complete and targeted PEs, and laboratory tests will be performed at regular intervals. A comprehensive PE will be conducted during the Screening visit, Day 1 and at the End of Study (EOS) visit. A targeted PE (general appearance, cardiovascular, respiratory and abdomen) will be conducted throughout the study as described in Schedule of Assessments ([Appendix 3](#)).

Any significant findings prior to administration of study drug will be considered as baseline conditions and if appropriate, will be captured as baseline medical history. Any medically significant changes from baseline will be monitored throughout the study and appropriate interventions will be taken accordingly. Clinical laboratory tests may be assessed at additional

times on unscheduled visits for safety reasons. Liver function abnormalities will be managed according to Drug-Induced Liver Injury (DILI) guidance ([Appendix 4](#)).

Adverse events, SAEs, and ongoing concomitant medication usage will be monitored and recorded throughout the study. Serious adverse event reports will be evaluated individually to assess for the impact of the event, if any, on the overall safety of the product and on the study itself. Cumulative AEs will be monitored throughout the study. Serious adverse events and AEs will be followed until resolved, stable, or until the subject's EOS visit. See [Section 9](#) for details on AE and SAE reporting.

An Independent Event Review Committee (IERC), blinded to treatment group, will adjudicate prespecified cardiovascular, cerebrovascular, and thromboembolic safety events of interest. These events include death from any cause, MI, stroke, congestive heart failure requiring hospitalization, unstable angina requiring hospitalization, deep venous thrombosis, pulmonary embolism, vascular access thrombosis and hypertensive emergency. A separate adjudication charter will describe the process in detail, and training and training materials will be provided to study sites.

